Appendix

Appendix 1:	Data Safety Monitoring Board (DSMB) Charter.....	21
Appendix 2:	MedWatch Form.....	21
Appendix 3:	Tacrolimus Extended Release (Astagraf XL®) Package Insert.....	21

List of tables

Table 1	Target Tacrolimus Extended Release Trough Levels.....	8
Table 2	Assessment Schedule.....	14

List of abbreviations

HS	Highly Sensitized
IVIG	Intravenous Immunoglobulin
PLEX	Plasma Exchange
SAEs	Serious Adverse Events
BPAR	Biopsy proven acute rejection
DSA	Donor Specific Antibodies
PRA	Panel reactive antibody
CSMC	Cedars-Sinai Medical Center
TMP/SMX	Trimethoprim/Sulfamethoxazole (Bactrim)
HLA	Human Leukocyte Antigen Antibodies
RIS	Relative Intensity Score
MFI	Mean Fluorescence Intensity
CRF	Case Report Form
SOC	Standard of Care
SAE	Significant Adverse Event
FDA	Federal Drug Administration
WHO	World Health Organization

Glossary of terms (correct format below)

Assessment	A procedure used to generate data required by the study
Control drug	A study drug used as a comparator to reduce assessment bias, preserve blinding of investigational drug, assess internal study validity, and/or evaluate comparative effects of the investigational drug
Enrollment	Point/time of patient entry into the study; the point at which informed consent must be obtained (i.e. prior to starting any of the procedures described in the protocol)
Investigational drug	The study drug whose properties are being tested in the study; this definition is consistent with US CFR 21 Section 312.3 and is synonymous with “investigational new drug.”
Medication number	A unique identifier on the label of each medication package in studies that dispense medication using an IVR system
Patient number	A number assigned to each patient who enrolls in the study. When combined with the center number, a unique identifier is created for each patient in the study.
Stage	A major subdivision of the study timeline; begins and ends with major study milestones such as enrollment, randomization, completion of treatment, etc.
Period	A minor subdivision of the study timeline; divides phases into smaller functional segments such as screening, baseline, titration, washout, etc.
Premature patient withdrawal	Point/time when the patient exits from the study prior to the planned completion of all study drug administration and assessments; at this time all study drug administration is discontinued and no further assessments are planned
Randomization number	A unique identifier assigned to each randomized patient, corresponding to a specific treatment arm assignment
Stop study participation	Point/time at which the patient came in for a final evaluation visit or when study drug was discontinued whichever is later
Study drug	Any drug administered to the patient as part of the required study procedures; includes investigational drug and any control drugs
Study drug discontinuation	Point/time when patient permanently stops taking study drug for any reason; may or may not also be the point/time of premature patient withdrawal
Variable	Information used in the data analysis; derived directly or indirectly from data collected using specified assessments at specified timepoints

Protocol synopsis

Title of study: A Prospective, Pilot Trial to Evaluate the Safety and Tolerability of Tacrolimus Extended-Release in HLA Sensitized Kidney Transplant Recipients

Purpose and rationale:

The purpose of this study is to demonstrate the safety of tacrolimus extended-release in HLA sensitized (HS, defined as panel reactive antibody $\geq 30\%$), kidney transplant recipients after desensitization with intravenous immunoglobulin (IVIG) and rituximab +/- plasma exchange (PLEX) per the standard of care with alemtuzumab induction.

Objectives:

The primary objective is to determine the safety of tacrolimus extended-release in the HS patient population as measured by the rate of serious adverse events (SAEs) and treatment failure. Treatment failure is defined as a composite of biopsy proven acute rejection (BPAR), graft failure, or death. BPAR is defined as \geq Banff 1A using the Banff 2007 criteria.

Secondary objectives are to observe the following:

1. Change in donor specific antibodies (DSA) as defined by the DSA relative intensity score[1,2]
2. Tolerability as defined by the number of subjects discontinuing the study medication

Population:

The study population will consist of HS patients (patients who have received desensitization) with end- stage kidney disease undergoing kidney transplantation. The study will begin at the time of transplantation while subjects are inpatients. They will be followed post- transplantation as outpatients.

Inclusion/Exclusion criteria:

Key **inclusion criteria** are as follows:

1. Recipient of a deceased or living donor kidney allograft
2. Patients must have undergone desensitization with IVIG and rituximab with or without plasma exchange prior to transplant or be administered IVIG and rituximab peri-operatively (within seven days of transplant) post-transplant
3. Age 18 and over
4. Able to understand and provide informed consent

5. At transplant, patient must have an acceptable crossmatch (as defined as T- or B- FCMX \leq 225 MCS) from non-HLA identical donor. Negative crossmatch is Tpronase FCMX <70; T- FCMX <50 and Bpronase FCMX <130; B-FCMX <100.

Key **exclusion criteria** are as follows:

1. Recipients of a dual simultaneous kidney/liver, kidney/heart, kidney/lung, or kidney/pancreas transplant
2. History of hypersensitivity to any of the study drug or to drugs of similar chemical classes
3. Patients being treated with drugs that are strong inducers or inhibitors of cytochrome P450 3A4
4. Patients with a clinically significant systemic infection within 30 days prior to transplant
5. Patients who have any surgical or medical condition that may affect absorption of drug, such as severe diarrhea, active peptic ulcer disease, or uncontrolled diabetes mellitus, which in the opinion of the investigator, might significantly alter the absorption, distribution, metabolism and/or excretion of study medication.
6. Women of childbearing potential who are either pregnant, lactating, planning to become pregnant during this trial, or with a positive serum or urine pregnancy test. Women of childbearing potential must be willing to agree to contraceptive practices.
7. Patients who are PCR positive for Hep B, Hep C, or HIV.

Investigational and reference therapy:

Tacrolimus extended-release starting dose 5mg once daily by oral administration adjusted to target trough level.

Table 1: Target Tacrolimus Extended-Release Trough Levels

Time	Tacrolimus
Day 4 to Month 6	7 – 9 ng/ml
Months 6-12	5 – 8 ng/ml

Study design:

This is a single center, pilot trial. It will be an open label, single-arm, non-controlled design. All HS patients age 18 and older requiring desensitization may be included in the study. Twenty subjects will be enrolled in the study. Subjects will take part in the study until they are one-year post-transplant. All subjects will require informed consent. At the time of screening, subjects will receive a physical exam and undergo lab testing as detailed below in the evaluation schedule. Alemtuzumab (Campath 1H, Lemtrada) will be administered to all subjects for induction immunosuppression immediately post-transplant. Maintenance immunosuppression will consist of tacrolimus extended-release, mycophenolate mofetil, and prednisone. Patients will receive antimicrobial prophylaxis as per Cedars-Sinai Medical Center (CSMC) protocol (valganciclovir x 6 months, TMP/SMX x 12months, and fluconazole x 1 month). Lab tests and physical exams for safety will take place according to the evaluation schedule below. Safety will be assessed by the reporting of serious adverse events as described below. Tacrolimus extended-release trough level, complete metabolic panel, complete blood count with differential, donor specific antibodies, and urinalysis with culture will be assessed according to the evaluation schedule below. Subjects will complete the study at one year post-transplant. Consent may be withdrawn by the study participant at any time. The investigator may also withdraw the study participant at any time if there are any safety concerns.

Efficacy assessments:

This is a pilot study and no efficacy assessments will be made.

Data analysis:

All outcomes will be reported as frequencies. Safety will be assessed by measuring the frequency of serious adverse events at one year post transplant. The frequency of BPAR, graft loss, and death will also be assessed at one year post transplant.

1 Background

Kidney transplantation remains the gold standard for the treatment of end-stage kidney disease. Advances in immunosuppression are integral to the success of kidney transplantation. Current immunosuppression regimens have reduced the number of rejections. However, long-term allograft survival remains a challenge. One limitation of immunosuppression regimens is the pill burden placed upon the recipients. This leads to long-term non-adherence and late rejections that ultimately place the allograft at risk^[1,2].

Approximately 30% of the patients currently awaiting a kidney transplant are broadly HLA-sensitized. These preformed HLA-antibodies create a difficult to match phenotype that results in a longer wait time for a kidney transplant and higher rates of rejection

after kidney transplant. Broadly HLA-sensitized patients are often excluded from clinical trials due to their extended length of time on dialysis (associated with increased post-transplant morbidity) and increased rates of rejection.

Tacrolimus twice daily is very effective in preventing allograft rejection and is administered as first line therapy as part of multidrug immunosuppression regimen. Tacrolimus twice daily has a narrow therapeutic index and frequent drug monitoring is necessary to maximize efficacy and prevent adverse effects. There is high intra-individual variability that can place the allograft at risk of deterioration due to rejection or toxicity^[3].

Tacrolimus extended-release (Astagraf XL, Astellas Pharma US, Inc., Northbrook, IL) is a once daily formulation of tacrolimus. It is currently approved for the prophylaxis of organ rejection in kidney transplant recipients. Short and long-term data support the efficacy and safety of the once daily formulation^[4, 5]. However, patients with a panel reactive antibody > 30% were excluded from the studies. It has therefore, not been studied in this patient population.

2 Purpose and rationale

The purpose of this pilot study is to determine safety and tolerability of tacrolimus extended-release in a population of HS renal transplant patients. Recipients will receive desensitization therapy consisting of IVIG and rituximab +/- PLEX per the standard of care at CSMC. All recipients will receive induction with alemtuzumab. Tacrolimus extended-release has not been studied in this patient population to date.

3 Objectives

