10.4.2 Safety

Safety variables to be assessed include discontinuation from study, discontinuation from treatment, renal function, SAEs, notable events, and laboratory tests. The number of serious adverse events will be reported as an observation since this is a pilot study. Safety data will be reviewed quarterly by a PI and designated Co-PIs.

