10.5 Sample size calculation

This is a pilot study therefore sample size calculation is not applicable. Twenty

patients will be enrolled.

11 Ethical considerations

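### The synopsis sets out to demonstrate safety, but 20 uncontrolled patients with no reference rate can only estimate event rates, and no interval is planned to show how imprecisely

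*Combined protocol and SAP*

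**What the plan says.** The synopsis, under purpose and rationale, states: "The purpose of this study is to demonstrate the safety of tacrolimus extended-release in HLA sensitized" recipients after desensitization. The rest of the protocol is more modest. The title uses *evaluate*. The synopsis objective and section 3.1 use *determine*, and the synopsis adds that safety is to be judged "as measured by the rate of serious adverse events (SAEs) and treatment failure". Section 2 reads: "The purpose of this pilot study is to determine safety and tolerability of tacrolimus extended-release in a population of HS renal transplant patients".

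On design, the synopsis says "It will be an open label, single-arm, non-controlled design" and "Twenty subjects will be enrolled in the study". Section 5 adds that patients who leave early are not replaced, and section 10.1 puts all enrolled patients in the analysis. Section 10.5 says: "This is a pilot study therefore sample size calculation is not applicable".

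On analysis, the synopsis says "All outcomes will be reported as frequencies". Section 10.4.1 plans frequencies and percentages and names Chi square and T-test. Section 10.4.2 says: "The number of serious adverse events will be reported as an observation since this is a pilot study".

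**The concern.** To demonstrate safety, a trial must be able to exclude some rate of harm that would be unacceptable. The visible text names no such rate, no external reference and no success criterion, and there is no control arm. No result could therefore meet or fail the purpose as the synopsis words it.

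The reporting plan adds to this. A count or percentage out of 20, given without an interval, does not show how wide a range of true rates is compatible with it. Section 1 says that sensitized patients have higher rejection rates and that the drug has not been studied in them. The uncertainty around each rate is therefore a substantial part of what this trial can report, and the plan does not provide for stating it.

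**Working it through.** **Plan's own figure.** The sample size of 20 cannot be reproduced. Section 10.5 gives no assumed rate, margin, power or target precision. For a declared pilot that is not in itself an error; it means only that the precision has to be worked out from n = 20.

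**Inputs.** n = 20 (synopsis; sections 4, 5 and 10.5). The outcome is a patient-level yes/no at one year, such as treatment failure. The event counts x below are illustrative, because the protocol gives no expected rates.

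**Formula.** The two-sided exact (Clopper-Pearson) 95% limits are:

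- lower = 0.025 quantile of Beta(x, n − x + 1), or 0 when x = 0
- upper = 0.975 quantile of Beta(x + 1, n − x)

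For x = 0 the upper limit reduces to 1 − 0.025^(1/n) = 1 − 0.025^(1/20) = 0.168.

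| Events / 20 | Observed | Exact 95% interval |
|---|---|---|
| 0 | 0% | 0 to 16.8% |
| 2 | 10% | 1.2 to 31.7% |
| 4 | 20% | 5.7 to 43.7% |
| 6 | 30% | 11.9 to 54.3% |
| 10 | 50% | 27.2 to 72.8% |

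The width at 4/20 is 43.7 − 5.7 = 38.0 percentage points. At 10/20 it is 72.8 − 27.2 = 45.6 points. Zero events is the most precise of these cases, and it is unlikely to be the relevant one for a composite that includes rejection in this population.

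**Sensitivity to convention.** For 0/20 the upper limit is 16.1% by Wilson, 15.0% by the rule of three (3/20) and 13.9% by a one-sided 95% exact limit, 1 − 0.05^(1/20). The conclusion is the same under each, but any figure written into the protocol should name its method and level.

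**Sensitivity to evaluable numbers.** Dropouts are not replaced, so one-year status may be unknown for some patients. The numbers here are assumed, not taken from the protocol. With 18 evaluable, the zero-event upper limit is 1 − 0.025^(1/18) = 18.5%. With 16 it is 1 − 0.025^(1/16) = 20.6%.

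**Chance of seeing nothing.** For an assumed true rate of 5%, P(0 events in 20) = 0.95^20 = 0.358. For an assumed 10%, it is 0.90^20 = 0.122.

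**The named tests.** Chi square and T-test need groups to compare or a reference value. Section 10.4.1 states neither and the trial has one arm, so these tests do not supply the missing statement of uncertainty.

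**The case against.** The strongest reply is that the point rests on a verb used once. *Demonstrate* occurs only in the synopsis purpose. The title, the objectives and section 2 are worded modestly, the study is called a pilot throughout, and section 10.4.2 already treats the serious adverse event count as an observation. A reader can also compute an interval from any x/20. Much of this stands. The wording problem is one synopsis sentence out of line with the rest of the protocol, not a concealed limit of the design. What it does not answer is that no interval and no precision statement is planned, whichever verb is used.

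Some stronger readings are tempting, but the documents do not support them:

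- *A reader might infer that section 10.5 dismisses precision.* It sets aside a sample size calculation and does not mention precision. A pilot needs no power calculation.
- *A reader might infer that no unsafe rate is defined anywhere.* Section 9.2 provides for quarterly board review with a letter on continuation, and the board's charter is an appendix whose content is not shown. One can say only that the visible text gives no threshold.
- *A reader might infer that a low count will be reported as proof of safety.* No section contains such a conclusion rule.

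One technical limit also stands. Binomial intervals apply to patients with at least one event, not to a total number of serious adverse events, which is what section 10.4.2 plans to report. The patient-level proportion is therefore an addition to that count and does not replace it.

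**Conclusion.** The point holds as one of wording and reporting. The synopsis purpose claims more than a 20-patient, single-arm trial without a reference rate can deliver, and it is out of line with the protocol's own title and objectives. The trial can estimate rates, with two-sided exact 95% intervals of 0 to 16.8% at 0/20 and 5.7 to 43.7% at 4/20. These figures assume 20 evaluable patients and independent patient-level outcomes; fewer evaluable patients would widen them.

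The documents do not support concluding that the trial is too small for a pilot or that its limits are hidden. Once the purpose is stated as estimation, no reference rate is needed to fulfil it. The gain from the change is modest but real, and it costs very little.

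**What to change.** 1. **Synopsis, purpose.** Change the stated aim to *estimate the rates of serious adverse events and treatment failure*, in line with the objectives.
2. **Synopsis data analysis and section 10.4.** Report the following as proportions with two-sided exact 95% confidence intervals: treatment failure, each of its components, patients with at least one serious adverse event (in addition to the planned event count), and patients discontinuing study drug. Do not rely on Chi square or T-test for this, since there is no comparison group.
3. **Section 10.5.** Keep 20 as a pilot size and add the expected precision with method and level, for example: *With 20 evaluable patients, the two-sided exact (Clopper-Pearson) 95% interval is 0 to 16.8% for 0 events and 5.7 to 43.7% for 4 events.*

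The cost is a few sentences, a few table columns and a visibly less precise conclusion. No extra patients, visits or data are needed.

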3.1 Primary objectives

The primary objective is to determine the safety of tacrolimus extended-release in HS kidney transplant recipients after desensitization with IVIG and rituximab +/- PLEX per the standard of care and alemtuzumab induction.

3.2 Secondary objectives

Secondary objectives are to observe the following:

1. Change in DSA as defined by the DSA relative intensity score (RIS) defined by: 0 points for no DSA, 2 points for each weak DSA (MFI <5,000), 5 points for each moderate DSA (MFI 5,000 -10,000), and 10 points for each strong DSA (MFI >10,000)^[1,2].
2. Tolerability as defined by the number of subjects discontinuing the study medication

4 Study design

The study will be a single center, pilot trial. It will be an open label, single-arm, non-controlled design. All HS kidney transplant recipients, age 18 and older, requiring desensitization may be included in the study. Initial desensitization protocol for LD or DD includes Intravenous Immunoglobulin (IVIG) 2g/kg (>70kg max 140g) given on day 0 (split over 2 days for peritoneal dialysis patients), rituximab 375mg/m² (rounded to the nearest 100mg vial) given on day 15, and IVIG 2g/kg (>70kg max 140g) given on day 30. Recipients for LD or DD who are unresponsive to IVIG/ritux (after 2 months for LD and after 6 months for DD) will require plasma exchange (PLEX) 5-7 sessions followed by IVIG 2g/kg (>70kg max 140g) and rituximab 375mg/m². Patients will be receiving acetaminophen, antihistamine, and steroid as premedication for all infusions.

A total of 20 subjects will be enrolled in the study. Subjects will take part in the study until they are one year post-transplant. All subjects will require informed consent. At the time of screening, subjects will receive a physical exam and undergo lab testing as detailed below in the evaluation schedule. Alemtuzumab (Campath 1H, Lemtrada) 30mg, will be administered subcutaneously to all subjects for induction immunosuppression immediately post-transplant. Maintenance immunosuppression will consist of tacrolimus extended-release, mycophenolate mofetil 500mg twice daily or mycophenolate sodium 360mg twice daily, and prednisone. Patients will receive antimicrobial prophylaxis per CSMC protocol. Lab tests and physical exams for safety will take place according to the evaluation schedule below. Safety will be assessed by the reporting of serious adverse events as described below.

Tacrolimus trough level, complete metabolic panel, liver function panel, complete blood count with differential, DSA, and urinalysis with culture will be assessed according to the evaluation schedule below. Subjects will complete the study at one year post-transplant. Consent may be withdrawn by the study participant at any time. The investigator may also withdraw the study participant at any time if there are any safety concerns.

Desensitization includes Intravenous Immunoglobulin (IVIG) 2g/kg (>70kg max 140g) given on day 0 (split over 2 days for peritoneal dialysis patients), rituximab 375mg/m² (rounded to the nearest 100mg vial) given on day 15, and IVIG 2g/kg (>70kg max 140g) given on day 30. Patients will require plasma exchange (PLEX) 5-7 sessions if they have received desensitization in the past. In this case, patients will receive PLEX daily x 5-7 sessions followed by IVIG 2g/kg (>70kg max 140g) and rituximab 375mg/m². Patients will be receiving acetaminophen, antihistamine, and steroid as premedication for all infusions.

5 Population

Male and female HS renal transplantation patients, 18 years of age and over, receiving a cadaveric or living donor kidney transplant may enter the study. Patients must

receive desensitization therapy. Twenty patients will be enrolled at CSMC for this pilot study. Patients who discontinue the study prematurely will not be replaced.

5.1 Inclusion Criteria

Patients eligible for inclusion in this study have to fulfill all of the following criteria:

1. Recipient of a deceased or living donor kidney allograft
2. Patients must have undergone desensitization with IVIG and rituximab with or without plasma exchange prior to transplant or be administered IVIG and rituximab peri-operatively (within seven days of transplant) post-transplant
3. Age 18 and over
4. Able to understand and provide informed consent
5. At transplant, patient must have an acceptable crossmatch (as defined as T- or B- FCMX ≤ 225 MCS) from non-HLA identical donor. Negative crossmatch is Tpronase FCMX <70; T- FCMX <50 and Bpronase FCMX <130; B-FCMX <100.

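### Does the absence of a PRA threshold from the numbered eligibility criteria leave the study population undefined?

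*Combined protocol and SAP*

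**What the plan says.** The synopsis uses HS in two ways. The purpose paragraph has "HS, defined as panel reactive antibody", followed by a threshold of 30% or more. The population paragraph has "The study population will consist of HS patients (patients who have received desensitization", with no threshold. The abbreviation list expands HS as highly sensitized, also without a threshold. The body of the protocol uses the term but does not define it again.

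The design text names HS and the need for desensitization together. The synopsis says "All HS patients age 18 and older requiring desensitization may be included in the study", and section 4 says "All HS kidney transplant recipients, age 18 and older, requiring desensitization may be included in the study". Section 5 opens with "Male and female HS renal transplantation patients, 18 years of age and over" as the people who may enter, and separately requires desensitization therapy. The primary objective in section 3.1 concerns safety "in HS kidney transplant recipients after desensitization with IVIG and rituximab".

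The numbered lists come next. Section 5.1 begins "Patients eligible for inclusion in this study have to fulfill all of the following criteria" and gives five items: donor kidney, desensitization, age, consent and crossmatch. Section 5.2 gives seven exclusions. No item names HS or PRA, and the synopsis lists are the same in this respect.

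PRA is not a named item in the assessment schedule (Table 2) or in the baseline data of section 7.1. Section 10.1 analyses everyone enrolled.

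**The concern.** The case for the trial rests on PRA. Section 1 says of the earlier studies of this drug: "However, patients with a panel reactive antibody > 30% were excluded from the studies". The trial is meant to supply data on the group those studies left out.

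If HS means PRA of 30% or more, that condition is missing from the list that is supposed to decide eligibility. If HS means having been desensitized, the trial could take patients whom the earlier studies did not exclude. A desensitized patient with PRA below 30% meets every numbered item and one of the two descriptions of HS, but not the other. Because PRA is not a named baseline variable, the report might not show how many of the 20 patients belong to the group in the rationale. A small uncontrolled series offers little beyond a clear account of whom it studied, so this deserves a check.

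**Working it through.** The plan gives no figure to reproduce, since section 10.5 fixes 20 patients without a calculation. The check is first on the text, then on how much a misclassified patient could matter.

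**1. Is there one population rule or two?**

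- Synopsis, purpose: the only sentence that says HS is defined as something. It names desensitization separately, as something done to HS patients.
- Synopsis, population: a parenthesis after HS patients. It can be read as a second definition or as a description of the HS patients this trial takes.
- Synopsis, study design, and section 4: HS and the need for desensitization appear side by side. If HS meant desensitized, one of the two would be redundant.
- Section 3.1: HS recipients, after desensitization. Again two attributes.
- Section 5: HS patients may enter, and they must also receive desensitization. Again two attributes.

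All of these except the parenthesis treat HS and desensitization as separate conditions. The coherent reading is that patients must be HS, with PRA of 30% or more, and must also be desensitized.

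**2. Is the HS condition missing from eligibility?**

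Items naming HS or PRA: 0 of 5 in section 5.1 and 0 of 7 in section 5.2. Both lists sit under section 5, whose opening sentence limits entry to HS patients. The condition is therefore stated in the parent section and not repeated as a numbered item.

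**3. Would PRA be recorded?**

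Section 7.1 collects the recipient's and donor's transplant background under an open-ended list. Table 2 has a standard-of-care row for transplant serology and donor background at the pre-op visit. Section 10.2 summarizes continuous baseline variables by sample size, mean, standard deviation, median, minimum and maximum. PRA fits these items, although none of them requires it by name.

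**4. How far could a result move?**

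Let k of the 20 enrolled patients have PRA below 30%. The documents give no value for k, and it may be 0. With event rates p(HS) and p(low) in the two groups:

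p(all) − p(HS) = (k/20) × [p(low) − p(HS)]

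For k = 1 the multiplier is 1/20 = 0.05, so even a rate difference of 100 percentage points moves the all-enrolled rate by 5 points. With an assumed difference of 20 points, the shift is 0.05 × 20 = 1 point.

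For scale, the exact (Clopper-Pearson) two-sided 95% interval for an assumed 4 events in 20 is 5.7% to 43.7%, a half-width of (43.7 − 5.7)/2 = 19 points.

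The exact 95% upper limit after zero events is 1 − 0.025^(1/n). For assumed sizes n of the PRA-defined group:

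| n | Upper limit | Change from n = 20 |
|---|---|---|
| 20 | 16.8% | – |
| 18 | 18.5% | 1.7 points |
| 15 | 21.8% | 5.0 points |
| 10 | 30.8% | 14.0 points |

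The change becomes large only if many enrolled patients are below 30%, and nothing in the documents points that way. These intervals are illustrative. The synopsis plans to report outcomes as frequencies, and the plan schedules no confidence intervals and no analysis by PRA.

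**The case for a change.** The strongest case for a change is that the text does contain two descriptions of HS, one a laboratory threshold and the other a treatment history, and the documents never say that they coincide. Pointing to section 5 does not fully settle this, because section 5 uses the same undefined term and the threshold appears only in the synopsis. The generic baseline items permit PRA to be recorded but do not require it. The repair would be cheap: one definition and one named field.

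Much of this stands as a description of the drafting. A strict reader could take the parenthesis as a definition, and the plan does not guarantee a PRA count in the report. There is also a trivial mismatch at exactly 30%: the synopsis definition includes that value, while section 1 speaks of earlier exclusions above it.

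What does not stand is the step from loose wording to a defect in the study. The argument needs low-PRA patients to be enrolled, and the documents do not suggest that they would be. IVIG and rituximab are given here because of HLA sensitization, so having received them is a reasonable proxy for HS. Nor does the argument identify a planned result that would come out differently. The point that a baseline variable is not ensured could be made of any variable that is not listed by name.

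**Conclusion.** No change to the plan follows. What remains is a drafting slip: a condition set out in the synopsis and in section 5 is not repeated in section 5.1, and a loosely worded parenthesis sits beside the one explicit definition. The site can apply the rule by reading the numbered list under its parent section. Analysts describing a sensitized cohort can be expected to tabulate baseline PRA with the other transplant characteristics under section 10.2.

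The possible effect is 5 percentage points of the denominator for each patient below 30%, with a count that may be zero. All enrolled patients are analysed whichever reading is taken, so no planned calculation changes.

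This conclusion rests on two assumptions: that desensitized patients at this center are in general sensitized at the stated level, and that PRA is available from the transplant work-up. The documents make both plausible and prove neither. If a substantial share of the 20 proved to have PRA below 30%, the report would have to say so when describing its population. The planned baseline summaries leave room for that.
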